4.5.3 Additional safety assessments

4.5.3.1 Clinical laboratory evaluations

Laboratory values, including markedly abnormal laboratory values will be presented descriptively by treatment group for the SS.

Tables presenting markedly abnormal values and those based on CTCAE grade (see section 6.13) will only include selected laboratory variables.

For tables where data are summarized by visit, unscheduled and repeat visits will not be summarized, but these data will be included in listings. Assessments collected at SFU visit should be included in by-visit tables. For tables where multiple measurements over a period of time are considered (as in shift tables), unscheduled and repeat visits will be considered as long

as they were collected in the period being summarized. All summaries will be presented in SI units and will be based on observed case values. In the case where laboratory values are below the lower limit of quantification, then these will be set to the midpoint between 0 and the lower limit of quantification for the purpose of summarizing the data. Only central laboratory results will be used in table analysis, while local laboratory results will only be displayed in listings.

For summaries for the ITP and Initial and Maintenance Period (combined) where multiple measurements across different visits are considered (as of markedly abnormal values tables, minimum/maximum post-baseline CTCAE tables, and shift tables), the laboratory results will be attributed according to their sampling date and time at risk for each period (see Section 4.5.1).

The following analyses will be presented:

- A summary of the absolute and change from Baseline values in each laboratory variable by treatment group and visit for the SS displaying the Placebo/BKZ 320mg Q4W and BKZ 320mg Q4W/Q8W.
- A summary of the number and percentage of study participants experiencing markedly abnormal values at any time while on treatment (ie, assessment on or following the first dose of IMP through the last dose of IMP + 119 days, occurring at scheduled and unscheduled visits) by laboratory variable and treatment group. Baseline values and values observed more than 119 days after the last administration of IMP are not considered. Two separate tables will show results for the ITP (for the SS) and the initial and maintenance treatment period (combined) (for the AMS). See section 6.10.1 for the criteria for markedly abnormal values.

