- A summary of the number and percentage of study participants with a given CTCAE grade (0,1,2,3, or 4) based on minimum/maximum post-baseline value by laboratory variable and treatment group. Two separate tables will show results for the ITP (for the SS) and the initial and maintenance treatment period (combined) (for the AMS).
- Shift tables of the number and percentage of study participants experiencing CTCAE grade 0,1,2,3, or 4 values (as applicable) at Baseline to minimum/maximum post-Baseline CTCAE grade, by laboratory variable and treatment group. Two separate tables will show results for the ITP (for the SS) and the initial and maintenance treatment period (combined) (for the AMS).
- By-study participant listings of all laboratory data (including urinalysis) will be provided. These listings will be presented by treatment group and will include: center, study participant identifier, age, sex, race, weight, visit, laboratory variable, result (with abnormal values flagged as “L” or “H” accordingly) and unit.
- A separate listing will be provided for laboratory results classified as Grade 3 or Grade 4 for the SS.

The table for markedly abnormal liver function tests (LFTs) will contain data beyond the CTCAE Grade 3 thresholds outlined in Section 6.10.1 in order to allow for a more thorough review of elevated LFTs. There will be one table which will list the count and percentage of study participants meeting the below criteria at any time during the study:

- AST: >3xUpper Limit of Normal (ULN), >5xULN, >8xULN, >10xULN, >20xULN
- ALT: >3xULN, >5xULN, >8xULN, >10xULN, >20xULN

- AST or ALT: >3xULN, >5xULN, >8xULN, >10xULN, >20xULN
- Bilirubin: >1.5xULN, >2xULN
- ALP: >1.5xULN

For any participant with at least one markedly abnormal LFT (AST >3xULN, ALT >3xULN, bilirubin >3xULN, or ALP >1.5xULN) the New Ratio (nR) will be calculated as the ratio of either maximum ALT or maximum AST (whichever is higher) to ALP, all expressed as multiples of their ULN as follows:

- $nR = [\text{maximum}(\text{ALT/ULN or AST/ULN})]/(\text{ALP/ULN})$

A plot displaying shift in liver function tests from baseline to maximum post-baseline result and a plot showing maximum post-baseline Total Bilirubin versus maximum post-baseline AST and ALT will be provided for the AMS if there are study participants with reported markedly abnormal LFT.

The following definition of potential drug induced liver injuries (pDILI) will be used (all criteria must be met at the same assessment):

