6.10 Appendix 10: Potentially Clinically Significant Criteria for safety endpoints

6.10.1 Criteria for Markedly abnormality for laboratory data

Markedly abnormal values are defined as those with a severity of Grade 3 and above based on the CTCAE criteria (U.S. Department of Health and Human Services 2010). Definitions of markedly abnormal values using the Grade 3 cut points are given in the tables below for age ranges of ≥ 17 years (Table 6-5 for markedly abnormal liver function test values, Table 6-6 for markedly abnormal biochemistry values, and Table 6-7 for markedly abnormal hematology values).

Table 6-5: Definitions of Markedly Abnormal Liver Function Values

| Parameter name | Conventional | | Standard | | Abnormal designation |
|----------------------|--------------|--------------------------|----------|--------------------------|----------------------|
| | Unit | Criteria | Unit | Criteria | |
| Alkaline Phosphatase | | $>5.0 \times \text{ULN}$ | | $>5.0 \times \text{ULN}$ | AH |
| ALT | U/L | $>5.0 \times \text{ULN}$ | U/L | $>5.0 \times \text{ULN}$ | AH |
| AST | U/L | $>5.0 \times \text{ULN}$ | U/L | $>5.0 \times \text{ULN}$ | AH |
| Total Bilirubin | mg/dL | $>3.0 \times \text{ULN}$ | umol/L | $>3.0 \times \text{ULN}$ | AH |
| GGT | U/L | $>5.0 \times \text{ULN}$ | U/L | $>5.0 \times \text{ULN}$ | AH |

Table 6-6: Definitions of Markedly Abnormal Biochemistry Values

| Parameter name | Conventional | | Standard | | Abnormal designation |
|----------------|--------------|--------------------------|----------|--------------------------|----------------------|
| | Unit | Criteria | Unit | Criteria | |
| Creatinine | mg/dL | $>3.0 \times \text{ULN}$ | mmol/L | $>3.0 \times \text{ULN}$ | AH |
| Glucose | mg/dL | <40 | mmol/L | <1.7 | AL |
| | | >250 | | >13.9 | AH |
| Calcium | mg/dL | >12.5 | mmol/L | >3.1 | AH |
| | | <7.0 | | <1.75 | AL |
| Potassium | mmol/L | >6.0 | mmol/L | >6.0 | AH |
| | | <3.0 | | <3.0 | AL |

| Parameter name | Conventional | | Standard | | Abnormal designation |
|----------------|--------------|--------------|----------|--------------|----------------------|
| | Unit | Criteria | Unit | Criteria | |
| Sodium | mmol/L | >155 <130 | mmol/L | >155 <130 | AH AL |
| Cholesterol | mg/dL | >400 | mmol/L | >10.34 | AH |

Table 6-7: Definitions of Markedly Abnormal Hematology Values

| Parameter name | Conventional | | Standard | | Abnormal designation |

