6.13 Appendix 13: Definition of CTCAE grades

Table 6-9: Definitions of CTCAE grades by biochemistry parameter

| Parameter (unit) | Definition | Unit | Grade 1 | Grade 2 | Grade 3 | Grade 4 |
|------------------|------------|--------|----------------|--------------------|--------------------|-----------|
| Creatinine | High | mmol/L | >ULN-1.5 x ULN | (>1.5 – 3.0) x ULN | (>3.0 – 6.0) x ULN | 6.0 x ULN |
| Sodium | Low | mmol/L | 130-<LLN | N/A | 120-<130 | <120 |
| Sodium | High | mmol/L | >ULN-150 | >150-155 | >155-160 | >160 |
| Potassium | Low | mmol/L | 3.0-<LLN | 3.0-<LLN | 2.5-<3.0 | <2.5 |
| Potassium | High | mmol/L | >ULN-5.5 | >5.5-6.0 | >6.0-7.0 | >7.0 |
| Calcium | Low | mmol/L | 2.0-<LLN | 1.75-<2.0 | 1.5-<1.75 | <1.5 |
| Calcium | High | mmol/L | >ULN-2.9 | >2.9-3.1 | >3.1-3.4 | >3.4 |
| Cholesterol | High | mmol/L | >ULN-7.75 | >7.75-10.34 | >10.34-12.92 | >12.92 |
| Glucose | Low | mmol/L | <LLN – 3.0 | <3.0 – 2.2 | <2.2 – 1.7 | <1.7 |
| Glucose | High | mmol/L | >ULN – 8.9 | >8.9 – 13.9 | >13.9 – 27.8 | >27.8 |

Note that high glucose values (hyperglycemia) are based on fasting glucose and in this study glucose is collected nonfasting.

Table 6-10: Definitions of CTCAE grades by hematology parameter

| Parameter (unit) | Definition | Unit | Grade 1 | Grade 2 | Grade 3 | Grade 4 |
|------------------|------------|--------------------|-----------------|------------------|---------------|---------|
| Hemoglobin | Low | g/L | 100-<LLN | 80-<100 | <80 | N/A |
| Hemoglobin | High | g/L | >0-20 above ULN | >20-40 above ULN | >40 above ULN | N/A |
| Platelets | Low | 10 ⁹ /L | 75-<LLN | 50-<75 | 25-<50 | <25 |
| WBC | Low | 10 ⁹ /L | 3-<LLN | 2-<3 | 1-<2 | <1 |
| WBC | High | 10 ⁹ /L | N/A | N/A | >100 | N/A |
| Lymphocytes | Low | 10 ⁹ /L | 0.8-<LLN | 0.5-<0.8 | 0.2-<0.5 | <0.2 |
| Lymphocytes | High | 10 ⁹ /L | N/A | >4-20 | >20 | N/A |
| Neutrophils | Low | 10 ⁹ /L | 1.5-<LLN | 1.0-<1.5 | 0.5-<1.0 | <0.5 |

Note that subjects who meet the decreased potassium criterion of 3.0< LLN, which is specified as the decreased potassium lab criterion for both CTCAE Grade 1 and Grade 2, will be counted as Grade 2.

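### The SI cut-off for markedly abnormal low glucose (<1.7 mmol/L) is the Grade 4 limit; it matches neither the SAP's Grade 3 rule nor the <40 mg/dL printed beside it.

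*SAP*

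**What the plan says.** SAP Section 6.10.1 sets the rule: "Markedly abnormal values are defined as those with a severity of Grade 3 and above based on the CTCAE criteria". It then says of its own tables: "Definitions of markedly abnormal values using the Grade 3 cut points are given in the tables below". In Table 6-6 of that section the low-glucose row is "Glucose | mg/dL | <40 | mmol/L | <1.7 | AL", with a conventional-unit limit and an SI limit side by side.

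The grades are defined in SAP Section 6.13. Table 6-9 gives, from Grade 1 to Grade 4, "Glucose | Low | mmol/L | <LLN – 3.0 | <3.0 – 2.2 | <2.2 – 1.7 | <1.7". Grade 3 is therefore 1.7 to <2.2 mmol/L, and Grade 4 is <1.7 mmol/L.

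SAP Section 4.5.3.1 says how the limits are used. On units: "All summaries will be presented in SI units and will be based on observed case values". For the markedly abnormal tables, one for the Initial Treatment Period (Safety Set) and one for the combined period (Active Medication Set), it points back to the appendix: "See section 6.10.1 for the criteria for markedly abnormal values". The same section also plans a summary by CTCAE grade, a shift table by grade, and a Grade 3/4 listing.

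**The concern.** One row breaks two rules at once. The SI limit should be the Grade 3 limit and should be the same concentration as the mg/dL limit next to it; it is neither.

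The column with the error is the one the summaries use. A participant whose lowest post-Baseline glucose is, say, 2.0 mmol/L would be Grade 3 in any output built on Table 6-9 but absent from the markedly abnormal count. Two outputs in the same report would then disagree about the same person, and the markedly abnormal table would understate low glucose. The SAP version history says the Amendment 2 edits to Sections 6.10 and 6.13, which added the glucose grades, were meant to make these two definitions agree.

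**Working it through.** **Inputs**
- Table 6-6, low glucose: <40 mg/dL and <1.7 mmol/L.
- Table 6-6, high glucose: >250 mg/dL and >13.9 mmol/L.
- Table 6-9, low glucose: Grade 3 starts below 2.2 mmol/L, Grade 4 below 1.7 mmol/L.
- Molar mass of glucose, about 180.16 g/mol (a physical constant), so 1 mmol/L = 18.016 mg/dL.

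**Step 1: the plan's own conversion.** The high-glucose pair reproduces: 250 / 18.016 = 13.88, which rounds to 13.9. It also gives a factor from the table itself: 250 / 13.9 = 17.99 mg/dL per mmol/L.

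**Step 2: convert the low-glucose pair.**

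| Conversion | With 18.016 | With the table's own 17.99 |
|---|---|---|
| 40 mg/dL to mmol/L | 2.22 | 2.22 |
| 1.7 mmol/L to mg/dL | 30.6 | 30.6 |
| 2.2 mmol/L to mg/dL | 39.6 | 39.6 |

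The stated 1.7 mmol/L is not reproduced from 40 mg/dL. The Grade 3 limit of 2.2 mmol/L is, to rounding.

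**Step 3: other conversions in Table 6-6.** Calcium (4.008 mg/dL per mmol/L): 12.5 / 4.008 = 3.12 against 3.1 printed, and 7.0 / 4.008 = 1.75 as printed. Cholesterol (38.67 mg/dL per mmol/L): 400 / 38.67 = 10.34 as printed. Low glucose is the only mg/dL-to-mmol/L pair that fails.

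**Step 4: compare each SI limit with the grade tables.**

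| Parameter (SI) | Markedly abnormal | Grade 3 begins | Grade 4 begins | Match |
|---|---|---|---|---|
| Creatinine high (x ULN) | 3.0 | 3.0 | 6.0 | Grade 3 |
| Sodium low | 130 | 130 | 120 | Grade 3 |
| Sodium high | 155 | 155 | 160 | Grade 3 |
| Potassium low | 3.0 | 3.0 | 2.5 | Grade 3 |
| Potassium high | 6.0 | 6.0 | 7.0 | Grade 3 |
| Calcium low | 1.75 | 1.75 | 1.5 | Grade 3 |
| Calcium high | 3.1 | 3.1 | 3.4 | Grade 3 |
| Cholesterol high | 10.34 | 10.34 | 12.92 | Grade 3 |
| Glucose high | 13.9 | 13.9 | 27.8 | Grade 3 |
| **Glucose low** | **1.7** | **2.2** | **1.7** | **Grade 4** |

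The eight haematology limits in Table 6-7 (haemoglobin low and high, platelets low, white cells low and high, lymphocytes low and high, neutrophils low) all equal the Grade 3 limits in Table 6-10. In total 17 of 18 match Grade 3; low glucose alone does not.

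**Step 5: what is missed.** With <1.7 mmol/L as the limit, the whole Grade 3 band, 1.7 to <2.2 mmol/L (about 30.6 to 39.6 mg/dL), is not flagged.

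**The case against.** The discrepancy itself is hard to dispute; the fair objections concern its weight.

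- **It touches one row of a descriptive table.** No hypothesis test uses it. Glucose is not among the safety topics of interest, and the only event of special interest is potential Hy's Law. The numerical laboratory criteria for discontinuing IMP in Protocol Section 7.1 do not use Table 6-6. Clinically significant laboratory changes are recorded as adverse events on the investigator's judgment, whatever this limit says. All of this stands.
- **Grade 3 values do not vanish.** They remain in the Grade 3/4 listing and in the listing of all laboratory data and, if glucose is included, in the grade and shift tables. This also stands, and it confines the undercount to the markedly abnormal tables.
- **The clash is conditional.** Section 4.5.3.1 restricts the markedly abnormal and CTCAE tables to selected variables without naming them. Glucose is probably among them, because it has a row in Tables 6-6 and 6-9, but that is an inference. A clash also needs at least one participant in the band. The documents give no expected frequency, and with about 120 participants there may be few or none.
- **A programmer might flag from the grade instead.** The text rule in Section 6.10.1 would then give the right count despite the table entry. That is possible, but Section 4.5.3.1 refers to the criteria in Section 6.10.1 and asks for SI units, so <1.7 mmol/L is the natural number to code.

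The note under Table 6-9 about nonfasting samples concerns high glucose and does not explain the low limit.

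**Conclusion.** The concern holds. The SI limit for markedly abnormal low glucose is the Grade 4 limit, contradicts the SAP's Grade 3 rule, and is not equivalent to the mg/dL limit in the same row. The grade comparison and the unit conversion both identify the SI entry as the wrong one.

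As written, the markedly abnormal tables for the Initial Treatment Period and the combined period would leave out every low-glucose value that is Grade 3 but not Grade 4. How many participants that affects cannot be estimated from the documents and may be none. The conclusion about outputs assumes that glucose is one of the selected variables and that the SI column is what is programmed. The result is a possible undercount in these tables and an inconsistency between safety outputs. It does not bear on the co-primary or key secondary analyses, the Type I error rate, the sample size or the management of participants.

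**What to change.** In SAP Table 6-6, change the SI criterion for low glucose from <1.7 to <2.2 mmol/L. The row then agrees with the Grade 3 rule, with Table 6-9 and, to rounding, with <40 mg/dL. This corrects a reporting threshold using the SAP's own grade table.

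The cost is one number in the SAP and one in the program. If the markedly abnormal tables have already been run, rerun both and check the glucose row against the Grade 3/4 listing over the same analysis set and period. Deriving the flag from the CTCAE grade where one exists would keep the two definitions from drifting apart again.

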6.10.2 Criteria for Markedly abnormality for vital signs data

The definitions of markedly abnormal vital sign values are provided below:

Table 6-8: Definitions of Markedly Abnormal Blood Pressure Values

| Parameter (unit) | Markedly Abnormal Low | Markedly Abnormal High |
|---------------------------------|---|---|
| Systolic blood pressure (mmHg) | <90 and a decrease from Baseline of ≥20 | >180 and an increase from Baseline of ≥20 |
| Diastolic blood pressure (mmHg) | <50 and a decrease from Baseline of ≥15 | >105 and an increase from Baseline of ≥15 |

For this summary, Baseline values and values observed more than 119 days after the last administration of study medication are not considered.

6.11 Appendix 11: Compliance

Due to the method of administration of the treatments, compliance will be examined in terms of completed injections.

Treatment compliance will be calculated as:

$$\frac{\text{total number of completed injections}}{\text{total number of expected injections}} \times 100\%$$

where the total number of expected injections is derived relative to when the study participant finishes treatment. In this study, Baseline visit and Weeks 4, 8, 12, 16, 20, 24, 28 are dosing visits. Two injections are administered at each given visit either with active dosing or placebo injection. It is expected that a study participant should complete total 16 injections by the end of study. If a study participant discontinues early, then the number of expected injections is based on the time of early discontinuation relative to the dosing visits. For example, if a study participant discontinues after Week 8 visit and prior to Week 12 visit, the total number of expected injections will be 6.

A summary of percent treatment compliance categorized as <75% and ≥75% will be provided by treatment group and study periods (ITP for the SS, MTP for the MS, and the Initial and Maintenance Treatment Period (combined) for the AMS).

A by-study participant listing of treatment compliance will be provided on the SS.

6.12 Appendix 12: MedDRA algorithmic approach to anaphylaxis

The SMQ Anaphylactic reaction consists of three parts:

- A narrow search containing PTs that represent core anaphylactic reaction terms (Category A – core anaphylactic reaction terms)

| |
|-----------------------------------|
| Anaphylactic reaction |
| Anaphylactic shock |
| Anaphylactic transfusion reaction |
| Anaphylactoid reaction |
| Anaphylactoid shock |
| Circulatory collapse |
| Dialysis membrane reaction |
| Kounis syndrome |
| Shock |
| Shock symptom |
| Type I hypersensitivity |

- A **broad search** that contains additional terms that are added to those included in the narrow search. These additional terms are signs and symptoms possibly indicative of anaphylactic reaction and categorized in B, C or D

■ Category B (Upper Airway/Respiratory Terms)

| | |
|-----------------------------|------------------------|
| Acute respiratory failure | Nasal obstruction |
| Asthma | Oedema mouth |
| Bronchial oedema | Oropharyngeal spasm |
| Bronchospasm | Oropharyngeal swelling |
| Cardio-respiratory distress | Respiratory arrest |
| Chest discomfort | Respiratory distress |
| Choking | Respiratory failure |

| | |
|------------------------|--------------------------------|
| Choking sensation | Reversible airways obstruction |
| Circumoral oedema | Sensation of foreign body |
| Cough | Sneezing |
| Cyanosis | Stridor |
| Dyspnoea | Swollen tongue |
| Hyperventilation | Tachypnoea |
| Irregular breathing | Throat tightness |
| Laryngeal dyspnoea | Tongue oedema |
| Laryngeal oedema | Tracheal obstruction |
| Laryngospasm | Tracheal oedema |
| Laryngotracheal oedema | Upper airway obstruction |
| Mouth swelling | Wheezing |

■ Category C (Angioedema/Urticaria/Pruritus/Flush terms)

| | |
|--------------------------|----------------------|
| Allergic oedema | Oedema |
| Angioedema | Periorbital oedema |
| Erythema | Pruritus |
| Eye oedema | Pruritus allergic |
| Eye pruritus | Pruritus generalised |
| Eye swelling | Rash |
| Eyelid oedema | Rash erythematous |
| Face oedema | Rash generalised |
| Flushing | Rash pruritic |
| Generalised erythema | Skin swelling |
| Injection site urticaria | Swelling |
| Lip oedema | Swelling face |
| Lip swelling | Urticaria |
| Nodular rash | Urticaria papular |
| Ocular hyperaemia | |

■ Category D (Cardiovascular/Hypotension terms)

| |
|------------------------------------|
| Blood pressure decreased |
| Blood pressure diastolic decreased |
| Blood pressure systolic decreased |
| Cardiac arrest |
| Cardio-respiratory arrest |
| Cardiovascular insufficiency |
| Diastolic hypotension |
| Hypotension |

- An **algorithmic approach** which combines a number of anaphylactic reaction symptoms in order to increase specificity. A case must include one of the following where both occur on either the same day as when an injection was administered or one day after, and for scenarios where two events must have been reported, both events must have occurred within one day of each other (as anaphylaxis is an acute event, imputed dates should not be used in the algorithmic approach):
 - A narrow term or a term from Category A;
 - A term from Category B - (Upper Airway/Respiratory) AND a term from Category C - (Angioedema/Urticaria/Pruritus/Flush);
 - A term from Category D - (Cardiovascular/Hypotension) AND [a term from Category B - (Upper Airway/Respiratory) OR a term from Category C - (Angioedema/Urticaria/Pruritus/Flush)]

6.13 Appendix 13: Definition of CTCAE grades

Table 6-9: Definitions of CTCAE grades by biochemistry parameter

| Parameter (unit) | Definition | Unit | Grade 1 | Grade 2 | Grade 3 | Grade 4 |
|------------------|------------|--------|----------------|--------------------|--------------------|-----------|
| Creatinine | High | mmol/L | >ULN-1.5 x ULN | (>1.5 – 3.0) x ULN | (>3.0 – 6.0) x ULN | 6.0 x ULN |
| Sodium | Low | mmol/L | 130-<LLN | N/A | 120-<130 | <120 |
| Sodium | High | mmol/L | >ULN-150 | >150-155 | >155-160 | >160 |
| Potassium | Low | mmol/L | 3.0-<LLN | 3.0-<LLN | 2.5-<3.0 | <2.5 |
| Potassium | High | mmol/L | >ULN-5.5 | >5.5-6.0 | >6.0-7.0 | >7.0 |
| Calcium | Low | mmol/L | 2.0-<LLN | 1.75-<2.0 | 1.5-<1.75 | <1.5 |
| Calcium | High | mmol/L | >ULN-2.9 | >2.9-3.1 | >3.1-3.4 | >3.4 |
| Cholesterol | High | mmol/L | >ULN-7.75 | >7.75-10.34 | >10.34-12.92 | >12.92 |
| Glucose | Low | mmol/L | <LLN – 3.0 | <3.0 – 2.2 | <2.2 – 1.7 | <1.7 |
| Glucose | High | mmol/L | >ULN – 8.9 | >8.9 – 13.9 | >13.9 – 27.8 | >27.8 |

Note that high glucose values (hyperglycemia) are based on fasting glucose and in this study glucose is collected nonfasting.

Table 6-10: Definitions of CTCAE grades by hematology parameter

| Parameter (unit) | Definition | Unit | Grade 1 | Grade 2 | Grade 3 | Grade 4 |
|------------------|------------|--------------------|-----------------|------------------|---------------|---------|
| Hemoglobin | Low | g/L | 100-<LLN | 80-<100 | <80 | N/A |
| Hemoglobin | High | g/L | >0-20 above ULN | >20-40 above ULN | >40 above ULN | N/A |
| Platelets | Low | 10 ⁹ /L | 75-<LLN | 50-<75 | 25-<50 | <25 |
| WBC | Low | 10 ⁹ /L | 3-<LLN | 2-<3 | 1-<2 | <1 |
| WBC | High | 10 ⁹ /L | N/A | N/A | >100 | N/A |
| Lymphocytes | Low | 10 ⁹ /L | 0.8-<LLN | 0.5-<0.8 | 0.2-<0.5 | <0.2 |
| Lymphocytes | High | 10 ⁹ /L | N/A | >4-20 | >20 | N/A |
| Neutrophils | Low | 10 ⁹ /L | 1.5-<LLN | 1.0-<1.5 | 0.5-<1.0 | <0.5 |

Note that subjects who meet the decreased potassium criterion of 3.0< LLN, which is specified as the decreased potassium lab criterion for both CTCAE Grade 1 and Grade 2, will be counted as Grade 2.

